7 DESIGN OF THE CLINICAL INVESTIGATION

7.1 Overall Clinical Investigation Design

The study is a prospective, randomized, control investigation designed for comparison of two groups for the reduction of respiratory distress in a CoViD-19 population, using gammaCore® Sapphire plus standard of care (active) vs. standard of care alone (SoC), the control group. The gammaCore® treatments will be used acutely and prophylactically.

Figure 1 Overall Design

7.2 Clinical Investigation Procedures and Definitions

Once the patient is admitted to the hospital, the institution shall follow their standard protocol for their CoVid-19 patients. The investigator shall administer the consent form, conduct the intake and randomize the patient 1:1 into each of the two study arms prior to baseline measurements. Once qualified, the patient shall be trained on the use of gammaCore® and provided an initial treatment. For every day the patient is in the hospital but not on mechanical ventilation, the administration of gammaCore®, prophylactically and acutely, will be recorded on the daily study log as per protocol treatment.

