6. Current implantation of an electrical and/or neurostimulator device, including but not limited to a cardiac pacemaker or defibrillator, vagal neurostimulator, deep brain stimulator, spinal stimulator, bone growth stimulator, or cochlear implant
7. Current implantation of metal cervical spine hardware or a metallic implant near the gammaCore® stimulation site
8. Belongs to a vulnerable population or has any condition such that his or her ability to provide informed consent, comply with the follow-up requirements, or provide self-assessments is compromised (e.g. homeless, developmentally disabled and prisoner)
9. Compromised access to peripheral veins for blood sampling.
10. Pregnant women
11. Patients with active cancer or those who have had recent cancer treatment

CLINICAL INVESTIGATION PROCEDURE OVERVIEW:

Enrollment / Admission Day - Day 0

Study patient must meet all of the following inclusion criteria and none of the exclusion criteria

- Patient must sign Informed Consent and witness to signature must occur
- Randomization – Upon meeting all eligibility requirements (including verification of +CoViD-19 testing), patient's will be randomized 1:1 into either the control group or the treatment group
- Intake Collection of:
 - Basic Demographics
 - Date of Birth (DOB), Race, Sex, Smoking Status, County/Region
 - Medications, Co-morbidities

- CoViD-19 Test Results (Positive / Presumed Positive)
- Study Measurements:
 - Height/Wt (BMI)
 - Temperature
 - Blood Pressure
 - O₂ Saturation
 - PaO₂/FiO₂ ratio
 - Shortness of Breath (Yes / No)
 - Cough (Yes / No)
- Clinical Labs
 - Immunokine panel (TNF-α, IL-1β, IL-6)
 - Frozen blood sample
 - Leukocyte flow cytometry
 - Pro-Calcitonin
 - CRP
 - Ferritin
 - D Dimer
 - Complete hematology panel (CBC with differential)
 - Comprehensive metabolic panel
 - Serum or urine hCG (for any woman who might be pregnant)
- Device training: Patient receives device training on gammaCore® Sapphire device and receives first treatment with trained study staff*
 - VNS Stimulation Supervised**, record date and times of stimulations
 - Daily Tx Log Completion
 - Oxygen Required, Oxygen level (%) based on device type (HFNC / NC / Bipap / Optiflow), Ventilator Dependence, Date and time of Ventilation, Patient discharge home, Date and time of Discharge, Survival
- Clinical Improvement Ordinal Scale
 - Adverse event assessment

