7.2.1 Schedule of Clinical Investigation Events

7.2.1.1 Intake / Admission (Day 0)

Upon hospital admission, after the patient and the Investigator have signed the Informed Consent Form, the patient will be randomized 1:1 into one of the two treatment arms. Patient's severity of condition will be classified based on age, co-morbidities, and oxygen saturation as moderate or severe. To prevent allocation bias, the patient will be assigned to the test or control arm of the study based on severity of classification in a 1:1 ratio. Thereafter, the study physicians and/or attending physicians participating in the study and if feasible, will conduct a complete physical examination and obtain vitals. Medical and demographic information in the EMR pertinent to this trial and the patient's treatment will also be captured into the CRFs.

The following Intake and collection of data will then be conducted:

- Intake Collection of:
 - Basic Demographics
 - Date of Birth (DOB), Race, Sex, Smoking Status, County/Region
 - Medications, Co-morbidities
 - CoViD-19 Test Results (Positive / Presumed Positive)
- Study Measurements:
 - Height/Wt (BMI)
 - Temperature
 - Blood Pressure
 - O₂ Saturation
 - PaO₂/FiO₂ ratio
 - Shortness of Breath (Yes / No)
 - Cough (Yes / No)
- Clinical Labs
 - Immunokine panel (TNF- α , IL-1 β , IL-6)
 - Frozen blood sample[†]
 - Leukocyte flow cytometry
 - Pro-Calcitonin

- CRP
- Ferritin
- D Dimer
- Complete hematology panel (CBC with differential)
- Comprehensive metabolic panel
- Serum or urine hCG (for any woman who might be pregnant)
- Device training: Patient receives device training on gammaCore® Sapphire device and receives first treatment with trained study staff *
 - nVNS Stimulation Supervised**
 - Study log completion: patient will record date and times of stimulations.
 - Daily Tx Log Completion
 - Oxygen Required, Oxygen level (%) based on device type (HFNC / NC / Bipap / Optiflow), Ventilator Dependence, Date and time of Ventilation, Patient discharge home, Date and time of Discharge, Survival
 - Clinical Improvement Scale
 - Adverse event assessment

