7.4.2 Inclusion Criteria

The patients have to meet all of the following criteria to be eligible to enter the investigation:

1. Patients (age 18 years and older) who have tested positive or suspected/presumed positive for CoViD-19 using PCR real-time test
2. Patients with cough, shortness of breath or respiratory compromise (RR>24/min, increased work of breathing)
3. O₂ Saturation less than or equal to 96% on room air or sensation
4. Agrees to use the gammaCore Sapphire device as per protocol and to follow all of the requirements of the study including recording required study data
5. Permission for early am blood draw to freeze for subsequent lab tests and sequencing as related to CoViD-19 sequelae
6. Patient is able to provide signed and witnessed Informed Consent

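### Day 0 measurements follow randomisation, the written Day 0 orders conflict, and the baseline definition gives controls no exact cut-off

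*Combined protocol and SAP*

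**What the plan says.** Section 7.2 has the investigator obtain consent and then "conduct the intake and randomize the patient 1:1 into each of the two study arms prior to baseline measurements". Device training and the first treatment follow. The same section opens with usual care: "Once the patient is admitted to the hospital, the institution shall follow their standard protocol for their CoVid-19 patients".

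Section 7.2.1.1 randomises 1:1 once consent is signed. It then says that "severity of condition will be classified based on age, co-morbidities, and oxygen saturation as moderate or severe" and that "the patient will be assigned to the test or control arm of the study based on severity of classification in a 1:1 ratio". Examination and vitals come after that, if feasible. Next comes "The following Intake and collection of data will then be conducted", which introduces a list of intake items (co-morbidities among them), study measurements (O₂ saturation among them) and labs, including "Serum or urine hCG (for any woman who might be pregnant".

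The Synopsis randomises "Upon meeting all eligibility requirements (including verification of +CoViD-19 testing") and lists intake, measurements and labs below that. Section 7.4.3 makes pregnancy an exclusion and requires all criteria to be satisfied before enrolment.

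Section 7.10.1.1 defines baseline, in general, as the latest available value preceding the first study treatment, and names screening and baseline as example occasions. The control arm receives no device treatment and no sham (Synopsis, overall design). Section 7.7.5 evaluates changes in oxygen support, O₂ saturation and shortness of breath, and considers whether cytokines fall or rise.

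**The concern.** A change outcome needs a start value that is obtained in the same way in both arms and is unaffected by the allocation. Three features of the text weaken this.

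- The Day 0 measurement set comes after allocation in a trial whose arms cannot be masked at the bedside. Whoever records the start value may know the arm. A laboratory result will not move for that reason, but a Yes/No entry for shortness of breath could.
- The sections cannot all be followed as written, so two coordinators could run Day 0 differently and both be compliant. The severity class used in assignment has no clear place in the sequence.
- The baseline rule is tied to an event that occurs in one arm only. The plan does not say which control value is the last eligible one.

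At stake is how the descriptive arm differences in change from baseline are read. No formal test is involved, because section 7.10.1.2 makes every comparison nominal.

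**Working it through.** The plan states no effect size, SD, event rate, alpha or power that bears on this point, so there is no figure of its own to reproduce. The check sets the sections side by side.

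**1. Day 0 order**

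| Source | Order as written |
|---|---|
| Section 7.2 | consent → intake → randomise → baseline measurements → training and first treatment |
| Section 7.2.1.1 | consent → randomise → classify severity → assign by severity → examination and vitals → intake, measurements, labs → training and first treatment |
| Synopsis | consent → eligibility met → randomise → intake, measurements, labs → training and first treatment |

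Intake is before randomisation in the first row and after it in the second. In all three rows the measurement set follows randomisation. That is the stated order, not a contradiction. In all three, the listed measurements and labs also precede the first stimulation.

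**2. Severity.** The class must exist before an assignment that depends on it, yet 7.2.1.1 states the 1:1 randomisation first. Two of the three inputs, co-morbidities and O₂ saturation, reappear on the list collected afterwards. Values may already be in hand: inclusion criterion 3 concerns a saturation "less than or equal to 96% on room air or sensation", several exclusions require a review of medical history, and 7.2.1.1 allows EMR data to be copied into the CRF. The plan does not say that such values are the ones to use.

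**3. Baseline cut-off**
- If study treatment means the device, the active arm's cut-off is the first stimulation on Day 0. Controls have no such event.
- If study treatment includes standard care for controls, section 7.2 starts that at admission. This differs from the active arm's cut-off and may fall before the Day 0 set is collected.
- The example occasions in the definition, and the single Admission/D0 column of Table 1, point both arms to Day 0. Neither says which Day 0 value counts in a control.

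**4. Pregnancy status.** The Synopsis randomises only after eligibility is met, pregnancy is an exclusion, and 7.4.3 requires eligibility before enrolment. Read together, these already put pregnancy status before randomisation. The position of hCG on the later lists is a matter of alignment only.

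**5. Scale**
- Reach: up to 60 patients (7.4.1), 20 already completed (7.10.4). 60 − 20 = 40, and 40/60 = 67%. This is an upper limit, since others may be enrolled but not completed.
- Outcomes: section 6 lists 10 clinical events. Three are evaluated as changes under 7.7.5: oxygen support, O₂ saturation and shortness of breath.
- Unit: one patient recorded differently in an arm of 30 is 1/30 = 3.3 percentage points. This shows the scale and does not estimate bias.
- Adjustment for severity class: assume half the patients are severe, the classes differ by d within-class SDs, and allocation is 1:1 within class. Total variance is 1 + d²/4, so the ratio of adjusted to unadjusted interval width is 1/√(1 + d²/4):
  - d = 0: 1.000 (0% narrower)
  - d = 0.5: 1/√1.0625 = 0.970 (3% narrower)
  - d = 1: 1/√1.25 = 0.894 (11% narrower)

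Both d and the half-severe split are assumptions. These figures describe the possible gain from adjusting, not harm from the Day 0 order.

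**The case against.** The strongest reply is that position on a list is not time of first knowledge. The lists under randomisation also contain the CoViD-19 result, which the Synopsis expressly requires beforehand, so they must at least partly record facts already known. This stands. A reader might infer that pregnant women can be randomised before testing, or that severity is assigned without its inputs. The documents support neither inference.

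A second reply is that controls do have a reference, because the example occasions in the definition and the shared Day 0 column provide one. This stands in part. It rules out the reading that controls have no baseline at all, but it does not supply a cut-off matching the active arm's.

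Third, the route to bias depends on facts the plan does not state. It does not say when the arm is disclosed, or whether shortness of breath is reported by the patient or judged by staff. Without a sham, later entries are also made with the arm known, so a new order protects only the start value. All of this stands and limits the weight of the point. It does not remove the advantage of a start value fixed before allocation.

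Fourth, the separate SAP (sections 7.10.1, 7.10.1.3 and 7.10.1.4), which is not among the documents supplied, may define baseline. It could settle the definition. It could not create pre-allocation values that were never taken, or reorder bedside procedures.

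Finally, a strict pre-randomisation baseline would discard the Day 0 values of patients who were measured as the protocol told sites to. That is correct, and the fix needs a fallback.

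**Conclusion.** The point holds. The protocol takes the Day 0 measurement set after allocation in a trial without sham. Sections 7.2 and 7.2.1.1 conflict on intake, and 7.2.1.1 randomises before the severity classification that determines assignment. The baseline definition gives controls only an approximate reference.

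The effect cannot be sized from the documents. It is probably small: everything happens within Day 0, laboratory values are not exposed to knowledge of the arm, and comparisons are nominal. The exposure is mainly in judgement-based start values, shortness of breath above all, and it assumes that the arm is known when they are recorded.

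A reader might go further and conclude that baseline is contaminated by the device. The documents do not support that: the measurements and labs are listed ahead of the first stimulation. The oxygen entries of the daily log and the clinical improvement scale are listed after it, but list position does not establish when they were taken.

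**What to change.** For remaining patients, reconcile the Synopsis, sections 7.2 and 7.2.1.1 and Table 1 to one order:

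1. consent;
2. eligibility confirmed, with pregnancy status included as the Synopsis and 7.4.3 already require;
3. severity class recorded on the CRF, with a statement that routine admission or EMR values may be used;
4. Day 0 measurements and blood draw;
5. randomisation within severity class;
6. device training in the active arm.

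In section 7.10.1.1 and the SAP, define baseline in both arms as the last value before randomisation. For patients enrolled under the current order who have no such value, use the Day 0 value as the fallback (in the active arm, one taken before the first stimulation). Report by arm how many patients rely on it.

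Adjust the nominal arm differences for the severity class used in assignment and, where measured, for the baseline value. This is a precision gain that may be small.

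The cost is wording changes, a reordered Day 0 checklist, one CRF field and a short same-day wait before randomisation. Patients already completed cannot be improved beyond the fallback.

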7.2.1 Schedule of Clinical Investigation Events

7.2.1.1 Intake / Admission (Day 0)

Upon hospital admission, after the patient and the Investigator have signed the Informed Consent Form, the patient will be randomized 1:1 into one of the two treatment arms. Patient's severity of condition will be classified based on age, co-morbidities, and oxygen saturation as moderate or severe. To prevent allocation bias, the patient will be assigned to the test or control arm of the study based on severity of classification in a 1:1 ratio. Thereafter, the study physicians and/or attending physicians participating in the study and if feasible, will conduct a complete physical examination and obtain vitals. Medical and demographic information in the EMR pertinent to this trial and the patient's treatment will also be captured into the CRFs.

The following Intake and collection of data will then be conducted:

- Intake Collection of:
 - Basic Demographics
 - Date of Birth (DOB), Race, Sex, Smoking Status, County/Region
 - Medications, Co-morbidities
 - CoViD-19 Test Results (Positive / Presumed Positive)
- Study Measurements:
 - Height/Wt (BMI)
 - Temperature
 - Blood Pressure
 - O₂ Saturation
 - PaO₂/FiO₂ ratio
 - Shortness of Breath (Yes / No)
 - Cough (Yes / No)
- Clinical Labs
 - Immunokine panel (TNF- α , IL-1 β , IL-6)
 - Frozen blood sample[†]
 - Leukocyte flow cytometry
 - Pro-Calcitonin

- CRP
- Ferritin
- D Dimer
- Complete hematology panel (CBC with differential)
- Comprehensive metabolic panel
- Serum or urine hCG (for any woman who might be pregnant)
- Device training: Patient receives device training on gammaCore® Sapphire device and receives first treatment with trained study staff *
 - nVNS Stimulation Supervised**
 - Study log completion: patient will record date and times of stimulations.
 - Daily Tx Log Completion
 - Oxygen Required, Oxygen level (%) based on device type (HFNC / NC / Bipap / Optiflow), Ventilator Dependence, Date and time of Ventilation, Patient discharge home, Date and time of Discharge, Survival
 - Clinical Improvement Scale
 - Adverse event assessment

* For those patients allocated to gammaCore (nVNS), the patient will be instructed by a study physician on the gammaCore® technique. They will be instructed to use it according to the specified protocol, which will be available at bedside. Re-training on the device or study log completion can occur at any time the patient requests further instruction or clarification and/or if research staff feels re-training is necessary during supervised stimulations.

Instructions for the use of the device will be kept in each patient's room and will not be re-used for any other patient, or removed from the patient room for any reason, throughout their study participation.

Study team will provide each patient with a laminated study log for individual patient room, each day, to log their treatments. This log will be cleaned for reuse each day for each patient, then discarded per institutional policy and will not be used by any other patient. A duplicate paper study log will be located on the outside of the room, whereas a trained study investigator will transpose the data entered on the log from the patient's room, onto a CRF, with their signature and date, each day while patient is on study.

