7.4 Selection of Population for the Clinical Investigation

7.4.1 Number of Patients

After the first 20 patients have been enrolled and completed the study at Allegheny General Hospital, the investigator will conduct an interim analysis and submit findings to the IRB for approval to increase the enrollment up to 60 patients (30 patients per arm). Up to 90 patients are expected to be screened.

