7.10.1.2 Summary Statistics

Data will be presented using summary statistics. For example, categorical data may be presented as proportions and counts; continuous data may be presented with the mean, median, minimum, maximum, and/or standard deviations. Kaplan-Meier methodology may be used to present time to event data. All comparisons between active and control groups are nominal in nature; confidence intervals and p-values may be presented, but are not intended for inferential purposes.

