7.10.3 Determination of Sample Size

This is one of the first studies of GammaCore Vagus Nerve Stimulation treatment in COVID-19. There is no published data on anticipated effect size in humans. Hence, a formal power analysis could not be done.

Data will be presented using summary statistics. For example, categorical data may be presented as proportions and counts; continuous data may be presented with the mean, median, minimum, maximum, and/or standard deviations. Kaplan-Meier methodology may be used to present time to event data. All comparisons between active and control groups are nominal in nature; confidence intervals and p-values may be presented, but are not intended for inferential purposes.

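### Allocation uses a moderate/severe class, but section 7.10 does not say whether arm comparisons account for it; naming severity-stratified estimates is a cheap improvement

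*Combined protocol and SAP*

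**What the plan says.** **Allocation.** Section 7.2.1.1 has each patient "classified based on age, co-morbidities, and oxygen saturation as moderate or severe" and then allotted to the device or control arm "based on severity of classification in a 1:1 ratio", with the stated purpose of preventing allocation bias. No cut-offs, rule for combining the three components, block size or algorithm are given. Two other places describe plain 1:1 randomisation without severity: the Day 0 paragraph of the synopsis, and section 7.2, where the investigator is to "randomize the patient 1:1 into each of the two study arms prior to baseline measurements".

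**Analysis.** Section 7.10 does not mention severity, strata, covariates or a stratified method. Its examples are that "categorical data may be presented as proportions and counts", that continuous data may be given as means, medians and standard deviations, and that "Kaplan-Meier methodology may be used to present time to event data". Section 7.10.1.2 calls all arm comparisons nominal. It permits intervals and p-values but disclaims inferential use. Section 7.10.1.3, on the analysis of objectives, only points to the SAP, which section 7.10.1 describes as a separate document.

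**Size.** Section 7.4.1 sets a ceiling of 60 patients, 30 per arm. Section 7.10.3 adds: "Hence, a formal power analysis could not be done".

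**The concern.** When allocation is balanced on a factor that predicts outcome, that factor contributes almost nothing to the chance difference between arms. A standard error that ignores the factor still counts its contribution, so the interval comes out wider than the design warrants.

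The protocol itself treats two of the three components as prognostic. Section 5.1 describes older patients and those with comorbidities as at higher risk of ventilation and death, and section 7.7.4 says comorbidities influence the course of the disease. With at most 60 patients and no power basis, the interval around each difference is the main thing a reader learns about effect size. If section 7.10 does not settle the method beforehand, the choice between adjusted and unadjusted estimates could also be made after results are seen, in a trial where treatment is visible to patients and staff.

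**Working it through.** **Inputs from the protocol.** Two severity classes, 1:1 allocation, 30 per arm (2 × 30 = 60). The plan has no power or precision figure to reproduce. It gives no event rates, standard deviations, stratum split or prognostic strength for severity.

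**Assumptions.** Equal strata (15 per arm per stratum), exact 1:1 balance within each, and the same risks in both arms. The risks are assumed and shown as a range.

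**Risk difference.** Let p1 and p2 be the risks in moderate and severe patients, and m = (p1 + p2)/2.
- The unadjusted analysis uses variance m(1 − m) per patient.
- The variance that applies under balance is the within-stratum mean, [p1(1 − p1) + p2(1 − p2)]/2.
- The unadjusted interval is too wide by the factor √(total/within).
- Half-width = 1.96 × √(2 × variance/30).

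| Assumed risk, moderate/severe | Total | Within | Within/total | Width factor | Half-width, unadjusted → stratified |
|---|---|---|---|---|---|
| 10%/20% | 0.1275 | 0.1250 | 0.98 | 1.01 | 0.181 → 0.179 |
| 10%/30% | 0.1600 | 0.1500 | 0.94 | 1.03 | 0.202 → 0.196 |
| 10%/40% | 0.1875 | 0.1650 | 0.88 | 1.07 | 0.219 → 0.206 |
| 10%/50% | 0.2100 | 0.1700 | 0.81 | 1.11 | 0.232 → 0.209 |

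For 5%/25% the ratio is 0.1175/0.1275 = 0.92, or about 4% too wide. With exact balance the Mantel-Haenszel estimate equals the crude difference, so only the standard error changes.

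**Mean difference.** Let R² be the share of outcome variance explained by severity. Adjusted width is about √(1 − R²) times unadjusted width, and the equivalent sample size is 60/(1 − R²). Coverage of the unadjusted 95% interval comes from 20,000 simulated trials per setting with 60 patients, half of them severe.

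| Assumed R² | Adjusted/unadjusted width | Equivalent N | Coverage, unadjusted |
|---|---|---|---|
| 0 | 1.00 | 60 | 95.0% |
| 0.05 | 0.97 | 63 | 95.7% |
| 0.10 | 0.95 | 67 | 96.2% |
| 0.20 | 0.89 | 75 | 97.3% |
| 0.30 | 0.83 | 86 | 98.1% |

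Coverage of the adjusted interval stays near 95% throughout.

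**Odds ratio, 10%/30%.** The unadjusted SE of the log odds ratio is √[2/(30 × 0.16)] = 0.645. The stratified SE is √{1/[(15/2)(0.09 + 0.21)]} = √(1/2.25) = 0.667. Stratifying raises the SE, so the precision argument does not carry over.

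**Is the class captured?** The Day 0 intake list (7.2.1.1), Table 1 and its footnotes (7.2.2), the patient characteristics (7.7.1) and the required records (7.9.2) contain no severity class. Age, comorbidities and saturation are collected, but the class cannot be rebuilt from them because no rule is stated.

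**The case against.** The strongest reply is that section 7.10 is a summary, that its wording is illustrative, and that the section meant to name comparison methods defers to a SAP not seen here. A reader might infer that the sponsor has decided to ignore severity. The documents do not support that: they are silent, and the SAP may already adjust. What stands is that nothing in the available text links the allocation factor to any comparison.

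Second, stratified allocation is not certain. Only one of the three descriptions mentions severity, and section 7.2 places randomisation before baseline measurements. This stands, and it makes the conservatism conditional. It does not show that stratification is impossible, because eligibility already calls for an oxygen saturation. Balance could also be lost later, since section 7.10.1.1 restricts the ITT set to patients with a verified treatment.

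Third, the comparisons are nominal, and an over-wide interval errs on the cautious side. A reader might infer a threat to error rates or power. There is none, because no alpha or power is set for these comparisons and the effect is over-coverage.

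Fourth, the gain may be trivial: 1% to 3% when the severe-stratum risk is 20% to 30% against 10%. That also stands. Nor would stratifying repair chance imbalance within a class.

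**Conclusion.** The point holds as a modest one. Severity is a stated allocation factor, and section 7.10 does not say whether comparisons account for it. If arms are balanced within severity and severity is prognostic, unadjusted intervals are about 1% to 11% too wide for risk differences over the assumed risks. For mean differences they are about 3% (1/0.97) to 20% (1/0.83) wider than adjusted ones over assumed R² of 0.05 to 0.30. If severity is not prognostic, nothing is lost. No size is claimed for time-to-event measures, and odds ratios are excluded.

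It would be going too far to say that the intervals are too wide as a matter of fact, or that the remedy is free because the class is already on file. The first depends on figures the protocol does not give, and the second finds no support in the data-collection lists. This is a cheap improvement in the precision of reported intervals.

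**What to change.** 1. Reconcile the Day 0 text of the synopsis, section 7.2 and section 7.2.1.1 on whether and how randomisation uses severity. State the rule that defines the two classes.
2. Add a CRF field for the severity class used at randomisation.
3. In 7.10.1.2/7.10.1.3 and the SAP, specify a Mantel-Haenszel risk difference stratified by severity for ventilation and death, and ANCOVA with severity class and baseline value for laboratory measures. Stratify any time-to-event test by severity. If a comparison is to stay unadjusted, give the reason.
4. Show the unadjusted summaries alongside.

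**Cost.** One added CRF field and a few sentences of text, with no extra patients. If the class was not kept for patients already randomised, it must be retrieved from randomisation records. The downside is sparse strata: with about 15 patients per arm per stratum, a 10% risk gives 15 × 0.10 = 1.5 expected events per arm in the moderate stratum. That is why the crude figures should stay in view.
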